6. EFFICACY ANALYSES

Efficacy analysis including primary, key secondary, secondary, and exploratory analysis will be performed primarily using the mITT set, with subjects grouped according to the treatment assigned at randomization. Available data from all randomized subjects regardless of adherence to the protocol will be included in the efficacy analyses; this includes data from subjects who discontinued study drug early but continued with study assessments. All efficacy data will be listed for the ITT set.

Unless otherwise noted, hypothesis testing and estimation of treatment effects will be performed with a mixed effect model for repeated measure (MMRM) that includes data from all three treatment arms (PM, PEOM, and Sham). The Sham arm will represent the pool of the two sham treatment groups: SM and SEOM (i.e., the two sham arms will be pooled into a single “control” group). All hypothesis tests for efficacy endpoints will be two-sided.

Unless otherwise noted, analysis of efficacy endpoints (primary, key secondary, secondary, and exploratory) in the overall population will be adjusted for the following randomization stratification factors (actual status) and baseline covariates:

For primary efficacy endpoint

- Presence of CNV in the fellow eye (yes; no)
- Baseline GA lesion area ($< 7.5 \text{ mm}^2$ or $\geq 7.5 \text{ mm}^2$)

For key secondary, secondary, and exploratory endpoints

- Presence of CNV in the fellow eye (yes; no)
- Baseline GA lesion area ($< 7.5 \text{ mm}^2$ or $\geq 7.5 \text{ mm}^2$)
- Baseline value of the endpoint

Of note, the randomization stratification factors were assessed at the screening visit. In the event of a change in status in the GA lesion area between the screening visit and the baseline visit (i.e., GA lesion area $< 7.5 \text{ mm}^2$ at screening to $\geq 7.5 \text{ mm}^2$) then the baseline status will be used.

If a statistical model is not directly specified and if necessary, data will be analyzed with the following approaches:

- For continuous endpoints, the MMRM analysis described for the primary endpoint in Section 6.2.2.
- For categorical or ordinal variables, a Cochran Mantel Haenszel (CMH) test with the baseline category status, presence of CNV in the fellow eye (yes or no), and baseline GA lesion area ($< 7.5 \text{ mm}^2$ or $\geq 7.5 \text{ mm}^2$) as stratification factors.

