6.2.2. Main Analysis of Primary Efficacy Endpoint

The primary endpoint will be analyzed in the mITT population with subjects grouped according to the treatment assigned at randomization.

A MMRM model will be used to analyze the primary endpoint. The analysis model will include treatment (PM, PEOM, sham), presence of choroidal neovascularization in the fellow eye at baseline (Yes, No) and baseline GA lesion area ($< 7.5 \text{ mm}^2$ or $\geq 7.5 \text{ mm}^2$) as fixed effects, time (study month, categorical) as a factor, the time \times treatment interaction term, and the baseline GA lesion area ($< 7.5 \text{ mm}^2$ or $\geq 7.5 \text{ mm}^2$) \times time interaction term. The least square [LS] mean change from baseline to Month 12 will be estimated from the model for each of three arms as well as the comparisons of each of the three arms to each other. For other time points of interest, LS mean change from baseline will be estimated and compared between treatments. For each estimated LS mean, the corresponding 95% CI will be presented based on the model. For the comparison of the LS means, the corresponding 95% CI and the 2-sided P-value along with the percentage difference (difference in LS means between the arms/the comparison group LS mean) will be

presented. A common unstructured covariance matrix will be used to model the within-subject errors, the sandwich estimator (Diggle, Liang, and Zeger 1994) will be used to estimate the standard errors of the fixed effects parameters, and the degrees of freedom will be partitioned into between-subject and within-subject portions. If there are convergence problems with the model, then a heterogeneous autoregressive (1) covariance matrix will be used. If convergence problems still exist, an autoregressive (1) covariance matrix will be used. The LS mean of the change from baseline in the total area of GA lesion(s) \pm the standard error will be plotted over time by treatment group.

The observed values for the total area of GA lesion(s) will be summarized by treatment group and visit for both the study and the fellow eye. Summaries will present the descriptive statistics for baseline, absolute values and change from baseline data by visit.

The mean change from baseline in the total area of GA lesion (s) in the study eye \pm the standard error will be plotted over time by treatment group.

All GA lesion (s) size data will be listed for the ITT set.

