6.2.3.1. Missing Data Analyses Based on Multiple Imputation

The following sensitivity analysis based on multiple imputation will be performed, as appropriate, using the same statistical approach as the one used in the primary analysis:

- Subjects with treatment discontinuation or study withdrawal assessed as potentially related to study drug or lack of efficacy will have missing data after the discontinuation or withdrawal imputed via a control-based imputation based on the sham control subjects. This will be based on the mITT set.
 - Subjects who discontinue the treatment or study due to reasons that are potentially related to study drug or lack of efficacy include
 - Subjects who discontinue due to ocular adverse event, adverse event related to treatment, or adverse event related to injection procedure
 - Subjects who withdraw consent due to lack of efficacy (specify field includes ‘Lack of efficacy’) or not otherwise specified as not related to efficacy (specify field includes “Not specified”)
- Subjects with a monotone missing data pattern due to treatment discontinuation or study withdrawal will have missing data after the last assessment explicitly imputed by multiple imputation using a tipping point analysis method assuming missing not at random (MNAR). This will be based on the mITT set.

Imputation for the non-monotone missing pattern (i.e., arbitrary missing pattern) will be performed prior to the multiple imputation for the monotone missing pattern (i.e., where a missing GA area measurement at a visit for a subject implies that GA area measurements at all subsequent visits for that subject are missing).

For the nonmonotone missing pattern, missing value(s) between two visits with measured GA area will be imputed using the monotone data MCMC method, which was first proposed by Li (1988) and Liu (1993) described the algorithm. Multiple imputation will then be carried out for monotone missing pattern.

The two imputation methods will be implemented in SAS using the three standard steps to generate inference from imputed data: imputation step, analysis step, and pooling step.

Details are illustrated with SAS codes in Section 1.2.2.

- The missing data are filled in 1000 times to generate 1000 complete datasets.
- The 1000 complete datasets are analyzed by using the same approach as for the analysis for the primary objective.
- The results from the 1000 complete datasets are combined for the inference.

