6.3.2. Main Analyses of Key Secondary Efficacy Endpoints

6.3.2.1. Monocular Maximum Reading Speed

Maximum reading speed will be calculated per MNRead or Radner user manuals, with no adjustment for reading inaccuracy. An additional step to cap resulting reading speed values at a maximum of 300 words per minute will be implemented. Values above 300 words per minute exceed values reported in the literature for adults with no vision impairment for MNRead (Calabrese et al. 2016) or Radner (Radner et al. 2002; Radner and Diendorfer 2014) assessments. Maximum reading speed will be calculated as the mean of the three highest nonzero reading speeds (or two, or one value, as available) (Baskaran et al. 2019; Patel et al. 2011), except when all words per minute are calculated as 0: then the maximum reading speed will be calculated as 0.

Monocular maximum reading speed in the study eye will be summarized and analyzed in a similar fashion as the primary efficacy endpoint using MMRM described in Section 6.2.2. The model will include treatment (PM, PEOM, Sham), presence of CNV in the fellow eye (yes or no), and baseline GA lesion area ($< 7.5 \text{ mm}^2$ or $\geq 7.5 \text{ mm}^2$) as fixed effects; baseline monocular maximum reading speed as well as the chart type (MNRead or Radner) as covariates, time (in months) as a factor; the time \times treatment interaction term as well as the baseline monocular maximum reading speed \times time interaction term.

The observed values for the monocular maximum reading speed will be summarized by treatment group and visit for both the study and the fellow eye. Summaries will present the descriptive statistics for baseline, absolute values and change from baseline data.

The mean change from baseline in the monocular maximum reading speed of the study eye \pm the standard error as well as the LS mean of the change from baseline in the monocular maximum reading speed of the study eye \pm the standard error will be plotted over time by treatment group.

In addition, the categorical changes (improvements of ≥ 20 to <40 , ≥ 40 to <60 , ≥ 60 and minimal/no change (-20 to 20), worsening of ≥ 20 to <40 , ≥ 40 to <60 , ≥ 60) for the study eye will be summarized by treatment group and visit.

The shift from baseline in the monocular maximum reading speed for the study eye categories over time will be presented by treatment group for the following categories:

- < 40 wpm
- 40 to < 80 wpm
- 80 to <160 wpm
- ≥ 160 wpm

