6.3.2.2. Mean FRI Index Score

The mean FRI Index score will be calculated per the scoring algorithm in the FRI Index user's manual.

The mean FRI Index score will be summarized and analyzed in a similar fashion as the primary efficacy endpoint using MMRM described in Section 6.2.2. The model will include treatment

(PM, PEOM, Sham), presence of CNV in the fellow eye (yes or no), and baseline GA lesion area ($< 7.5 \text{ mm}^2$ or $\geq 7.5 \text{ mm}^2$) as fixed effects; baseline mean FRI Index score and baseline study eye status (Better-seeing Eye vs. Worse-seeing Eye) as covariates, time (in months) as a factor; the time \times treatment interaction term as well as the baseline mean FRI Index score \times time interaction term.

The observed values for the mean FRI Index score will be summarized by treatment group and visit. Summaries will present the descriptive statistics for baseline, absolute values and change from baseline data.

The mean change from baseline in the mean FRI Index score \pm the standard error as well as the LS mean of the change from baseline in the mean FRI Index score \pm the standard error will be plotted over time by treatment group.

In addition, the mean FRI Index score will be converted to the FRI Level variable, as per the user manual, ranging from 1 (Unable to do) to 4 (Totally independent). The categorical changes from baseline (improvements (an increase in FRI level), minimal/no change (no change in FRI level), and worsening (decrease in FRI level)) will be summarized by treatment group and visit. The shift from baseline in the FRI level over time will be presented by treatment group.

All FRI data will be listed for the ITT set.

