1.2.1 Mixed Effect Model for Repeated Measure

```
*-----  
* Read Analysis data  
*-----  
* In this example, repeated measures are available at  
* avisitn = 0.5 (baseline), 2 (Month 2),  
* 6 (Month 6), and 12 (Month 12)  
*-----;  
  
data ga;  
  set adam.adga;  
  if paramcd = 'SEGAORG' and  
  avisitn in (0.5, 2, 6, 12) and  
  ANL01FL = 'Y';  
  
  * trtan (actual treatment[number])  
  * 1 = APL-2 Monthly  
  * 2 = APL-2 Every Other Month  
  * 3 = pooled Sham group;  
  if trtan in (4,5) then trtan = 3;  
  
  * trt01 are trt02 are used in multiple imputation  
  * trt01 = 1 if Sham group  
  * trt02 = 1 if APL2 Monthly group  
  * trt01 = trt02 = 0 for APL2 EOM group;  
  if trtan = 3 then trt01= 1; else trt01 = 0;  
  if trtan = 1 then trt02= 1; else trt02 = 0;  
  
  * avisitc will be used in PROC TRANSPOSE;  
  if avisitn = 0.5 then avisitc = '00'; * Baseline;  
  if avisitn = 2 then avisitc = '02'; * Month 2;  
  if avisitn = 6 then avisitc = '06'; * Month 6;  
  if avisitn = 12 then avisitc= '12'; * Month 12;  
run;  
  
*****;  
*** MAIN ANALYSIS using MMRM ***;  
*****;  
  
proc mixed data=ga method=reml covtest empirical;  
  where avisitn NE 0.5; * exclude rows for baseline;  
  * cnv (CNV in the fellow eye)  
  * 0 = No  
  * 1 = Yes;  
  *base cat (baseline lesion size (<7.5 vs. ≥ 7.5));  
  class trtan cnv avisitn usubjid base_cat;  
  model chg = trtan cnv base_cat avisitn trtan*avisitn base_cat*avisitn  
  /cl;
```

```
repeated avisitn / subject=usubjid type=un r;  
lsmeans trtan*avisitn/pdiff cl e alpha=.05;  
ods output diffs= diff1 LSMeans= LSMean1;  
run;
```

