  by imputation_;
  class trtan;
  var cnv v00 -- v12;
  monotone reg(/details);
  mmar model(v02 -- v12 / modelobs= (trtan='3'));
run;

*****;
*** Delta-Adjusted Pattern Imputation (impute monotone missing) ***;
*****;
**First identify the subjects in the active treatment groups that we want to
apply the shift parameter if they have monotone missing data;
data ga_t_mono2;
  set ga_t_mono;

  **This is just an example of a reason that we do not want to
  apply the shift parameter. The actual reasons are in the text;
  if DCSREAS1 = "Death" then flag = 1;
  else flag = 0;
```

```
        if trtan in (1,2) and flag = 0 then adjustthis = 1;
        else adjustthis = 0;
    run;

proc mi data=ga t_mono2 out=ga_t_tip6 nimpute=1 seed=9484353;
  by _imputation_;
  class trtan adjustthis;
  var cnv trtan v00 -- v12;
  monotone reg(/details);
  mnar adjust(v02 / shift=0.12 adjustobs=(adjustthis = '1' ))
  adjust(v06 / shift=0.12 adjustobs=(adjustthis = '1' ))
  adjust(v12 / shift=0.12 adjustobs=(adjustthis = '1' ));
run;

*****;
*** SAS macro to run MIANALYZE on outputs from MMRM *;
*****;

%macro mi_results(in, lsm, dif);

* After imputation, the data sets are in the wide format in which
different variables (V00--V12) represent the outcome measured at
different occasions. Before analyzing using PROC MIXED,
the data sets need to be converted into long format in which one
variable represents all outcome with different values of AVISITN
differentiating different occasions;

proc transpose data= &in
  out= ga mi (rename= ( NAME = AVISITN COL1 = AVAL));
  by _imputation_ usubjid trta trtan trt01 trt02 param paramcd base base_cat;
  var V00 -- V12;
run;

data ga mi;
  set ga mi;
  label AVISITN = 'AVISITN';
  chg = aval - base;
  * baseline record is not used in MMRM;
  if AVISITN = 'V00' then delete;
run;

proc sort; by _imputation_; run;

proc mixed data=ga_mi method=reml empirical;
  by _imputation_;
  class trtan cnv avisitn usubjid base_cat;
  model chg=trtan cnv base cat avisitn trtan*avisitn base_cat*avisitn / cl;
  repeated avisitn / subject=usubjid type=UN;
  lsmeans trtan*avisitn / pdiff cl alpha=.05;
  ods output diffs= diffs lsmeans= lsmeans;
run;

* In the final step, the analysis results obtained from PROC MIXED
procedure are combined into a single estimation with standard error
using PROC MIANALYZE;
```

```
proc sort data=lsmeans;
  by avisitn trtan _imputation_;
run;
proc mianalyze parms=lsmeans;
  by avisitn trtan;
  modeleffects trtan*avisitn;

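### Optional efficiency gain: the primary MMRM adjusts for baseline GA area only through the 7.5 mm² category, although the continuous value is in the dataset

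*SAP*

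**What the plan says.** SAP Section 6 gives one covariate list headed "For primary efficacy endpoint", with fellow-eye CNV and the two-level GA area category. A second list, for the key secondary, secondary and exploratory endpoints, adds the endpoint's own baseline value.

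SAP 6.2.2 follows the first list. Its covariates are "presence of choroidal neovascularization in the fellow eye at baseline (Yes, No) and baseline GA lesion area", the last in two levels, with category-by-time and treatment-by-time interactions. The sample code agrees: "model chg = trtan cnv base_cat avisitn trtan*avisitn base_cat*avisitn" in Appendix 1.2.1, and the same terms, ending "avisitn trtan*avisitn base_cat*avisitn / cl", in the analysis step of 1.2.2. Section 6.2.3.1 ties the two together: "The 1000 complete datasets are analyzed by using the same approach as for the analysis for the primary objective".

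The continuous value is at hand. After imputation the data are reshaped by "usubjid trta trtan trt01 trt02 param paramcd base base_cat", the change score is computed from `base`, and the imputation models use the measured baseline area.

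Six other MMRMs (6.3.2.1, 6.3.2.2, 6.3.2.3, 6.4.1, 6.4.3, 6.4.4) keep the category and add their own continuous baseline with a time interaction. Reading speed, for example, uses "baseline monocular maximum reading speed as well as the chart type (MNRead or Radner) as covariates", and the FRI uses "baseline mean FRI Index score and baseline study eye status".

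**The concern.** Cutting a continuous covariate in two discards information. If larger lesions grow faster or slower within each category, that part of the variation stays in the residual and the treatment contrast has a wider standard error than the collected data require.

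The comparison with something to gain is PEOM against sham, planned at 81.5% power with SD 1.50. PM against sham, which alone decides whether the study is positive (SAP 6.2.1), is planned at 99.2%. PEOM still matters downstream. Under SAP 6.3.1, formal testing of the key secondary endpoints requires both primary hypotheses to be rejected in both studies, or both in APL2-303 for the fallback sequence.

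**Working it through.** **Inputs from the documents.** Mean growth 1.47 (PM), 1.70 (PEOM) and 2.13 (sham) mm²/year, so differences of 0.66 and 0.43; SD 1.50, 1.40 or 1.25 mm²; 200 per group (SAP 3.4). Alpha is 0.0495 in the planning table and 0.0496 at Month 12 (SAP 6.2.1). Eligible baseline area is 2.5–17.5 mm².

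**Inputs the documents do not give.** The correlation r of baseline area with 12-month growth, the baseline distribution, the shape of the relation, and whether SD 1.50 is raw or already covariate-adjusted. These are assumed below.

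**Reproducing the plan.** Noncentral t with 600 − 3 = 597 df and noncentrality d/(SD·√(2/200)). For PEOM at SD 1.50 this is 0.43/(1.50 × 0.1) = 2.867. At alpha 0.0495 the power is 81.5%, 86.5% and 92.9% at SD 1.50, 1.40 and 1.25, and 99.2% for PM at SD 1.50. All match SAP Table 1. At alpha 0.0496, PEOM at SD 1.50 is 81.6%.

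**What the cut keeps.** The share of baseline variance captured by the category is q = p(1−p)(m₁−m₀)²/Var(X), where p is the proportion at or above 7.5 mm² and m₁, m₀ are the category means. I used 21 assumed distributions truncated to 2.5–17.5 mm²: uniform; log-normal with median 6, 7, 8 or 9 and log-SD 0.4, 0.5 or 0.6; normal with mean 7.5, 8, 8.5 or 9 and SD 3.5 or 4. Over these, q runs from 0.554 to 0.687, so 31–45% of the variance is lost.

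**Linear relation, SD 1.50 as the raw SD.** Residual SD is 1.50·√(1−q·r²) with the category and 1.50·√(1−r²) with the continuous value added. At r = 0.5 and q = 0.554 these are 1.392 and 1.299, giving 86.9% and 91.0%. PEOM power at alpha 0.0496:

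| r | Category only | Plus continuous | Gain (points) |
|---|---|---|---|
| 0.1 | 81.8% | 81.9% | 0.1–0.2 |
| 0.2 | 82.4–82.6% | 83.1% | 0.5–0.7 |
| 0.3 | 83.5–83.9% | 85.0% | 1.1–1.5 |
| 0.4 | 85.0–85.8% | 87.7% | 1.9–2.7 |
| 0.5 | 86.9–88.1% | 91.0% | 2.9–4.1 |
| 0.6 | 89.2–90.9% | 94.7% | 3.8–5.5 |

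At r = 0.5 the gain is 2.3–3.3 points with SD 1.40 and 1.3–1.9 with SD 1.25. PM gains at most about 0.2 points.

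**SD 1.50 as the residual SD after the category.** The continuous term then reduces it to 1.50·√[(1−r²)/(1−q·r²)]. At r = 0.5 this is 1.400–1.427, and PEOM power goes from 81.6% to 85.2–86.5%, a gain of 3.6–5.0 points. For PM, Table 1 itself shows 99.2% at SD 1.50 and 99.7% at SD 1.40, so the gain is still no more than about half a point.

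**Other shapes** (raw SD 1.50; correlation of growth with the true function of baseline 0.3 / 0.5), PEOM gain in points:
- logarithmic: 0.8–1.2 / 2.1–3.3
- plateau above 10 mm²: 0.2–0.8 / 0.6–2.2
- inverted U peaking at 10 mm²: 0–0.9 / 0–2.4
- step at 7.5 mm²: 0 / 0

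**Check on validity.** In simulation (4,000 trials per setting, Month 12 ANCOVA, sandwich standard errors), the null rejection rate was 4.3–5.3% with the category and 4.4–5.5% with the continuous term added, with a Monte Carlo SE of 0.3 points. Under a step at 7.5 mm² the standard-error ratio was 1.000, so the extra term cost nothing measurable.

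These figures are for Month 12 alone and ignore missing data and the repeated measures.

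**The case against.** The strongest reply is that nothing is wrong. The category is the randomization stratum, and text, code and design agree. The protocol names baseline lesion area without fixing its form, and the SAP says that it supersedes the protocol's analysis plan. All of that stands. A reader might infer from the other six MMRMs that the SAP contradicts itself. It does not: Section 6 sets two separate lists, and 6.2.2 follows its own.

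The second reply is that no benefit is shown. That also stands. The gain is 0.1–0.2 points at r = 0.1 and nil for a step at 7.5 mm². A reader might equally take some figure in the table as a ceiling. It is not one, because both a higher r and the other reading of SD 1.50 give more. That makes the gain less certain, not more important.

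The third reply is that the change has side effects, and this is the most useful. The category is not constant in a lesion-size tertile that spans 7.5 mm². The percent-change endpoints in 6.2.7.2 inherit the primary model. Section 6 makes 6.2.2 the default for continuous endpoints without a model of their own. Arm LS means, and the percentage difference built on them, depend on the baseline value at which they are evaluated. The fix covers each of these.

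**Conclusion.** The point holds as an optional improvement that uses data already collected. The primary analysis as written gives a valid treatment contrast with no bias and no type I error inflation, and the 81.5% and 99.2% figures stand because they use no covariates. Reading this as a misspecified model or an overstated power would go beyond what the documents support.

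The size is conditional: for PEOM, from near zero to a few points of power, by the assumptions set out above. PM and the study's positive/negative decision are practically untouched. I would adopt the term, or record why the category alone was preferred.

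**What to change.** Before unmasking, and keeping the category and its time interaction:

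- Add continuous baseline GA area and its interaction with time to the primary covariate list in Section 6 and to the model in 6.2.2. It then carries to 6.2.6 and 6.4.2.
- Add `base` and `base*avisitn` to both MODEL statements (1.2.1 and 1.2.2), leaving `base` out of CLASS.
- Do not put the continuous term in place of the category. If growth steps at 7.5 mm², replacement would lose about 1.2 points of PEOM power at correlation 0.3 and 3.2 at 0.5; keeping both loses essentially nothing.
- 6.2.7.1: use the square root of baseline area.
- 6.2.7.2: state the covariate form, or keep the category-only model, since baseline is the denominator of the response.
- 6.2.5: the category drops out only where it is constant (the two 7.5 mm² subgroups and any tertile wholly on one side of the cut). The continuous term stays in all lesion-size subgroups.
- Limit the new term to GA-area endpoints, so that endpoints using 6.2.2 by default do not inherit it.
- State the baseline value at which arm LS means and the percentage difference are evaluated. The treatment contrast does not depend on it.
- Leave the slope models in 6.2.4.3 unchanged, because baseline area is one of the responses there.

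The cost is SAP wording and two lines of code, with no new data. The term uses about 6 degrees of freedom through Month 12 (six FAF visits) and about 12 through Month 24, among about 600 subjects.
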